In previous work, we demonstrated in one primarily Latino, urban sample, that text messaging by family members can be used to rapidly identify members with ILI/acute respiratory infections (ARI) early in an illness.¹⁸ This approach to early identification would enable implementation of an educational intervention targeted to the 36-hour timeframe. Providing education within a text message is a proven successful strategy to influence behavior.¹⁹⁻²² Using text message surveillance to trigger a novel educational intervention also allows inclusion of both medically and non-medically attended index cases, a key element in reducing influenza SAR since less than one-third of persons with laboratory-confirmed influenza seek medical care.¹⁸ Text messaging itself is scalable, low-cost, and can be used in low literacy populations.²³ However, using text-message based surveillance to trigger a real-time text-message behavioral educational intervention to decrease household influenza transmission has not been assessed. In evaluating the impact of this intervention strategy, the primary outcome will be laboratory-confirmed influenza. The primary outcome will be determined using self-swabs among household members to detect SAR, including asymptomatic infection and medically- and non-medically attended illness. We have successfully piloted self-swab collection.

Aim: To assess the impact of an educational intervention delivered by text messaging on transmission of influenza within households

Primary Outcome Hypothesis: Educational text-messages will reduce laboratory-confirmed influenza household transmission from 12% to 5%

Secondary Outcome Hypothesis: Educational text-messages will reduce ILI transmission from 23% to 11%

Exploratory Aim: To compare the yield of text message ILI/ARI surveillance among subgroups in a diverse, community sample

Hypothesis: Response rates to text messages will be similar among different sociodemographic groups.

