We will enroll and randomize 400 households (n=~1500 individuals) with ≥ 1 child recruited from four contiguous communities in New York City 1:1, stratified by community, to receive surveillance-only vs. surveillance plus text message educational intervention. We will have 88% power to detect a decrease in influenza SAR from 12% to 5%. These percentages are derived from the paper by Cowling *et al.*, reporting a reduction from 12% to 5% between hand hygiene and usual care arms in SAR for influenza when a non-text message-based behavioral intervention was started ≤ 36 hours of index illness onset.¹⁶ For surveillance, households in both arms will receive text messages 3x/week during each influenza season (Nov-Mar) and report household members with ILI/ARI symptoms. For those in the educational intervention arm, when an ILI/ARI is reported, educational text messages will be sent targeted to decrease household transmission.

Both arms will obtain one self-swab of the index case, and self-swabs of all other household members on days 3 and 5 from index onset.^{7,10,13,24} Swabs will be returned via postage-paid envelope and analyzed using an FDA-approved reverse-transcriptase multiplex PCR assay to identify influenza, including sub-types, as well as other viral respiratory pathogens, e.g., parainfluenza etc. We will also collect symptom reports from all household members. The primary outcome will be SAR of laboratory-confirmed influenza. Secondarily, we will assess SAR based on ILI/ARI symptoms, and of non-influenza viruses. Response rates will be compared between arms and by demographic factors (age, education, race/ethnicity). Trial results could provide support for text-based strategies to reduce influenza transmission.

B. RESEARCH STRATEGY

SIGNIFICANCE

Impact of Influenza: Influenza infection results in an estimated 31 million outpatient visits, 55,000 to 974,200 hospitalizations (2014-15 estimate: 974,206), and 3000 to 49,000 deaths (2014-15 estimate: 49,006) annually.¹⁻³ The burden of influenza also includes high cost from direct medical expenses, days lost from work or school,²⁵ and inappropriate use of antibiotics.²⁶ Children and adolescents 6 months-18 years old are at increased risk of influenza morbidity and mortality, and influenza is one of the most common causes of hospitalization for the pediatric population.¹ School-aged children and adolescents also serve as an important reservoir, transmitting influenza to household members.^{1,27}

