As part of an ongoing community-based study funded by CDC, we have demonstrated the feasibility of using text messaging to conduct ILI/ARI surveillance in one primarily Latino, urban neighborhood community.¹⁸ During the first three years of the study, 62,650 text messages were sent to households and responses were received for 48,308 (77.1%). The response rate did not decrease over time. The majority (88.9%) of responses

were received within 4 hours of messages being sent and 96.2% responses were received within 12 hours (section- preliminary studies). Based on our community study, the CDC has now included the use of text message surveillance as part of their pandemic influenza research plans.³⁷

Text Message Reporting and Real-time Behavioral Intervention to Reduce Transmission. While text messaging surveillance can rapidly assess if someone in a household is ill, one potential benefit of this type of surveillance that has not yet been studied is the ability to trigger a real-time educational intervention to decrease transmission by exploiting this rapid identification in order to decrease transmission from both medically-attended and non-attended index cases. Providing education within a text message is a proven successful strategy to influence behavior. We have demonstrated the impact of text message educational reminders to improve influenza vaccination as well as other vaccinations.¹⁹⁻²² Text messaging has also been used for other behavioral interventions such as smoking cessation.³⁸

The **Health Belief Model** provides a conceptual basis for the intervention we are proposing to test.^{39,40} According to this model, four main factors affect health-related behaviors: perceived susceptibility of

Figure 1: Health Belief Model and Behavioral Intervention to Decrease Respiratory Virus Transmission (modified from Rosenstock et al)

contracting the disease; perceived severity of the disease; perceived barriers to adoption of a behavior to avoid the disease; and the perceived effectiveness of the behavior. While the model is usually focused on an individual's behavior to protect him/herself from developing a disease, for infection transmission, the model can also include behaviors to protect oneself and other household members. Lastly, a cue to action must be present to trigger the behavior.

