Annual home visits will be made to all enrolled households wanting to continue the next respiratory season to facilitate retention and participation, answer questions, ensure contact information remains correct, update household composition changes, and provide swab kits. Households that continue to meet eligibility criteria (Table 2) may continue into the next respiratory season. Households will receive \$50 on enrollment and \$25 at this re-enrollment visit; this will aid with enrollment and retention. Participants will also receive compensation for reporting and returning self-swabs as outlined below. If a household no longer meets eligibility criteria during a season or if are lost to follow-up, we will replace households in the same season if there are ≥2 months left in the influenza season or the next year if there are <2months left. Households that leave the study will be replaced using the same procedures as for the baseline sample using 1:1 randomization. Based on previous studies, we expect 10-20% of households to be replaced yearly.^{18,29,67}

TEXT MESSAGE SURVEILLANCE FOR ILI/ARI

Both arms (surveillance + education vs. surveillance-only) will receive text messages to perform surveillance of household members for ILI/ARI. The surveillance period will run November through March each year. We have chosen that period since for the past 9 years (with the exception of the 2009 influenza A H1N1 pandemic) the earliest onset of influenza in these communities has been in November and we have seen the vast majority of influenza cases by March.^{18,68} If there are unusual influenza patterns, we will be able to start sample collection earlier or end it later. During the surveillance period, each household reporter in all households will automatically receive text messages three-times a week from the text messaging system (a.k.a. *research staff-generated messages*) asking if any household member has symptoms included in the study case definitions for ILI/ARI and asked to respond whether or not anyone is ill (Figure 3). Households will be texted on a Monday, Wednesday and Friday schedule to optimize days between reporting. We have chosen this schedule so that intervention can start within 36 hours of onset. Messages will be sent in English or Spanish based on the

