We will use Pearson chi square to assess relationship between text message response rates and community, reporter's race/ethnicity, insurance and education. This will be defined as number of responses received per message sent. If more than one variable is significantly related to reporting rates ($p<0.1$), we will develop multivariable logistic models to assess this relationship. We will also assess response rates by arm.

SAMPLE SIZE AND POWER

We have based our sample size on the primary outcome. With 200 households per arm and an average of 3.8 persons/household, we will have 88% power to detect a decrease in secondary attack rates of laboratory-confirmed influenza from 12% (surveillance-only) to 5% (surveillance + education), based on type I error of 5% and an intracluster correlation coefficient of 0.29. The intracluster correlation, expected transmission rates for the surveillance-only arm, and effect size are derived from the paper by Cowling *et al.*, reporting a reduction from 12% to 5% between the hand hygiene and usual care arms in SAR when a non-text message based behavioral intervention was started at ≤ 36 hours of illness onset in the index case using laboratory-confirmed influenza as an outcome.¹⁶ In the MoSAIC study, secondary attack rates for laboratory-confirmed influenza have been 16.6% therefore an expected rate of 12% in the surveillance-only arm is conservative. We will also be powered for our secondary outcome; we will have 91% power to detect a decrease in symptomatic ILI/ARI from 23% to 11%.¹⁶ If we lose 80 households (20%) per season, we will still have at least 80% power to detect the decreases in both the primary and secondary outcome as above, even without household replacement.

POTENTIAL CHALLENGES AND SOLUTIONS Table 3

Challenge	Solution
1. Recruitment and retention	In our previous community studies retention was excellent. In our MoSAIC study, 75.9% of households recruited in year 1 were still in the study in year 3.
2. Non-representative sample	Since eligibility criteria include ≥ 3 members and ≥ 1 child, the sample will not be fully representative of the communities. However, the benefits of these inclusion criteria include higher likelihood of infection and transmission.
3. Reporting bias	3x/a week texting will decrease recall bias. We have shown under- and over-reporting to be low and confirmed the validity of household symptom self-reports.

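### Text response rate per message sent stops counting households once texting ends, so subgroup or arm differences in dropout can be partly or fully hidden

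*Combined protocol and SAP*

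**What the plan says.** The exploratory hypothesis in the Specific Aims is "Response rates to text messages will be similar among different sociodemographic groups". The trial summary in the same section adds "Response rates will be compared between arms and by demographic factors (age, education, race/ethnicity". The Exploratory Aim in the Statistical Plan will use Pearson chi-square to "assess relationship between text message response rates and community, reporter's race/ethnicity, insurance and education", and response will also be assessed by arm. On the measure itself it says "This will be defined as number of responses received per message sent".

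The paragraph on annual home visits, after Randomization Procedures, governs who is in the denominator. Later seasons include only households that wish to continue and still qualify. Households lost to follow-up or no longer eligible are replaced in the same season if at least two months remain, otherwise the next year: "Households that leave the study will be replaced using the same procedures as for the baseline sample using 1:1 randomization". The expected volume is that "we expect 10-20% of households to be replaced yearly".

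The checks on replacement households (indicator variable, originally randomised sample only, worst case) are described under the transmission aim. The Exploratory Aim has no retention measure and does not say how replacements are handled.

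**The concern.** The exploratory aim asks about the yield of text surveillance across diverse groups. The Innovation section ties it to feasibility and scalability with less staff contact than in the team's previous study. For that purpose, a household that gives up on the system is an important form of non-response. With messages sent as the denominator, a household stops counting when its messages stop, and a newly recruited household's replies take its place. The subgroup and arm comparisons are thus conditional on still being texted. Groups that leave at different rates could show similar response rates, and the trial could report similar response where sustained reach differs.

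A smaller mismatch sits beside this. The Specific Aims list age as a comparison factor, and the Exploratory Aim's list omits it.

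**Working it through.** **Inputs from the documents**
- Reply rate: 48,308 / 62,650 = 0.7711, which reproduces the stated 77.1% (Preliminary Studies 2.1). Used as r = 0.771 while a household is engaged.
- Yearly loss: 10-20% overall. Giving one group d = 0.10 and another d = 0.20 is illustrative.
- Prompts: three a week, November to March. 151 days / 7 x 3 = 64.7, so 65 per season.
- Contact after one month without a report (Table 3): about 13 prompts. Same-season replacement needs two months left: about 26 prompts.

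**Assumptions**
- A leaver replies at r until it falls silent, at a time uniform over the 65 prompts, and is texted for L further prompts.
- It is replaced if at least 26 prompts remain, by a household that also replies at r.

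**One season, per scheduled prompt, original households**

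A leaver is engaged for 32 of 65 prompts on average (32/65 = 0.492). Rate = r x [(1 - d) + 0.492d].
- d = 0.10: 0.771 x 0.9492 = 73.2%
- d = 0.20: 0.771 x 0.8985 = 69.3%
- Gap: 3.9 points

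**One season, per message sent**

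For each leaver's place, replacement included, let S be the mean number of prompts sent and A the mean number sent while someone was engaged. Rate = r x [65(1 - d) + A d] / [65(1 - d) + S d].

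| Texting stops after silence of | S | A | d = 0.10 | d = 0.20 | Gap visible |
|---|---|---|---|---|---|
| 0 prompts | S = A | S = A | 77.1% | 77.1% | 0 |
| 13 prompts (one month) | 60 | 48.2 | 0.771 x 63.32/64.5 = 75.7% | 0.771 x 61.64/64 = 74.3% | 1.4 |
| 26 prompts (two months) | 60 | 39 | 0.771 x 62.4/64.5 = 74.6% | 0.771 x 59.8/64 = 72.0% | 2.5 (unrounded rates) |
| Never within the season | 65 | 32 | 73.2% | 69.3% | 3.9 |

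**Three seasons, losses only between seasons**

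Per scheduled prompt, rate = r x [1 + (1 - d) + (1 - d)^2] / 3.
- d = 0.10: 0.771 x 2.71/3 = 69.6%
- d = 0.20: 0.771 x 2.44/3 = 62.7%
- Gap: 6.9 points

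Per message sent, every household still texted replies at r, so both groups show 77.1% and none of the gap is visible.

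**The case against.** **Silence is counted.** Prompts go automatically to all households, and staff contact follows a month without reports, so about 13 unanswered prompts enter the denominator before that contact is due. A reader might infer that full disengagement never enters the measure. The documents do not support that. Nor does the available text say when a household counts as lost, when its texts stop, or that its past messages are removed. If texting runs to season end, the two measures agree within the season. This stands, and it limits the within-season claim to partial masking of unknown size.

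**The size is assumed.** No passage says that subgroups or arms differ in dropout, and 10-20% is an overall expectation. This stands.

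**The previous study does not prove masking.** In MoSAIC, "The response rate did not decrease over time", while Table 3 reports that "In our MoSAIC study, 75.9% of households recruited in year 1 were still in the study in year 3". A reader might multiply 0.759 by 77.1% to get 58.5% and call that the true rate. That applies a three-year pooled rate to the year-3 stayers and treats every leaver as a non-responder, although no reasons for leaving are given. The two figures show only that a stable per-message rate can coexist with attrition. They do not show that a group difference was hidden.

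**Leaving is not the same as not replying.** Some exits reflect lost eligibility, and later seasons are by re-enrolment. Counting all prompts never sent as unanswered would mix mobility with texting behaviour. This is a good reason not to replace the defined rate, which is transparent and comparable with the 77.1% benchmark. It is not a reason to omit retention, because the aim concerns yield and scalability.

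**Partial cover exists.** The Missing Data paragraph will classify missingness by variable and arm and relate it to demographics. It sits under the transmission aim and does not alter the response-rate comparison.

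**Conclusion.** The concern holds in limited form. The planned comparisons describe response among households still being texted, and nothing in the Exploratory Aim separates that from differential dropout. Masking can be anything from none to complete within a season, depending on when texting stops, and it is complete for exits between seasons. The illustrative gaps are 3.9 points in one season and 6.9 points over three. They rest on an assumed 10% versus 20% yearly loss, equal reply rates while engaged (replacements included), uniform timing of silence in the one-season case, and loss only between seasons in the three-season case. The mismatch on age is a plain inconsistency. The aim is exploratory and the transmission outcomes are untouched, so this is a minor point.

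**What to change.** In the Exploratory Aim of the Statistical Plan:

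- Keep replies per message sent as the defined rate, and state there when texting to a household stops.
- Add a supporting analysis by subgroup and arm, restricted to originally randomised households. It should give retention, and replies divided by all surveillance prompts scheduled within each season entered and also across the planned seasons.
- In that supporting rate, count prompts after withdrawal or loss to follow-up as unanswered. Censor, or report separately, households that leave because they no longer qualify. Exclude replacement households.
- Conclude that response is similar only if both measures agree.
- Add age to the factor list to match the Specific Aims, and say whose age is meant, since the Specific Aims do not.

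This follows the plan's statement that analyses are by randomised arm. The cost is some wording and a little more analysis from the message log and enrolment records. Age is already collected in the surveys. The available text does not say that exit dates and reasons are recorded, so that should be confirmed. The supporting rate will look lower than the per-message rate.

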Drs. [name], [name] and [name] have also worked closely with [name], the statistician for this study and for the MoSAIC project. Additionally, [name] collaborated with [name] on a project assessing predictors of influenza.⁶¹ His work with [name] has included analysis of knowledge, attitude and practice surveys, epidemiology studies, and interventional studies. [name] also has a history of collaboration with [name], a co-investigator, as they co-direct a CDC-funded research program to assess adverse events post-vaccination using text messaging surveillance.⁶²⁻⁶⁴ [name] works with [name] who helps oversee the laboratory component of the MoSAIC study. Drs. [name] and [name] collaborated with [name] on the NIH-funded ACURI study.⁵⁴ [name] is the Director of Columbia University's Community Pediatrics program and an expert in cultural competency and health literacy. [name] has worked previously with [name], an advisor; they both serve on the Steering Committee of Columbia University's Patient-Centered Outcomes Research Initiative. [name] has a long-standing relationship with [name], including 8 publications. [name] is a founding member of the Communities of Harlem Health Revival, a coalition of 72 community and faith-based organizations that seeks to improve the health of urban residents in upper Manhattan, and will aid recruitment.

OVERVIEW: We propose to conduct a randomized controlled trial of real-time text message-based educational intervention to reduce transmission of laboratory-confirmed influenza in 400 households sampled from four diverse, contiguous urban communities in New York City. The primary outcome is household transmission of laboratory-confirmed influenza. The secondary outcome is household transmission of symptomatic ILI/ARI and of non-influenza respiratory viruses among household contacts of index cases.

PRELIMINARY STUDIES

1. Recruitment of Participants to Clinical Studies Including Trials in Our Setting.

1.1 MoSAIC: MOBILE SURVEILLANCE FOR ARI/ILI IN THE COMMUNITY (U01 IP000618):¹⁸ Drs. [name], [name] and [name] recruited 158 households (84.5% of 187 households approached) in year 1 and 175 additional households in subsequent years 2-4 from one of the communities proposed in this study. The current surveillance population is over 1200 people. Many households recruited in year 1 are still in the study in year 4. Near all (99%) of the study population are Latino, and 72% are Spanish-speaking.

1.2 APPROPRIATE CARE OF URIs IN CHILDREN OF LATINO IMMIGRANTS: THE ACURI PROJECT (RC1MD004109):⁵⁴ Drs. [name] and [name] recruited 355 households, including 1460 individuals, from one of the communities in this proposed study. The mean number of people per household was 4 (range, 2 to 8 members) and nearly all (94%) households were retained through an 8-month study period. Near all (92%) of the study population are Latino, and 87% were Spanish-speaking.

1.3 IMPACT OF NON-PHARMACEUTICAL INTERVENTIONS ON URIs AND INFLUENZA IN CROWDED, URBAN HOUSEHOLDS (U01 CI000442):²⁹ [name] recruited 509 households, including 2788 individuals. The mean number of household members was 4.5, and mean duration of participation was 55.5 weeks with an 87% retention rate. Most (96%) individuals were Latino.

1.4 EFFECT OF ANTBACTERIAL HOME CLEANING AND HANDWASHING PRODUCTS ON INFECTIOUS DISEASE SYMPTOMS (R01NR05251):⁵⁵ [name] recruited 238 households, including 1178 persons. The mean number of household members was 5 (range, 3 to 13 members). Retention rates through the 48-week study were 94.1%. Most (98%) individuals were Latino.

2. ARI/ILI SURVEILLANCE IN A COMMUNITY-BASED SAMPLE AND TEXT MESSAGING SURVEILLANCE

2.1 MoSAIC: MOBILE SURVEILLANCE FOR ARI/ILI IN THE COMMUNITY:¹⁸ Drs. [name], [name], and [name] have used text messaging to conduct surveillance for ARI/ILI. During the first three years of the study, 62,650 text messages were sent to households; responses were received for 48,308 (77.1%). The response rate has not decreased over time. The majority (88.9%) of households who responded did so within 4 hours of messages being sent; 96.2% responded within 12 hours. The median time from symptom onset to research-assistant obtained nasal swab is 2 days; 75-80% of specimens were collected within the optimal 48-72 hour window.¹⁸

2.2 APPROPRIATE CARE OF URI IN CHILDREN OF LATINO IMMIGRANTS: THE ACURI PROJECT:⁵⁴ Drs. [name] and [name] conducted illness surveillance in household using weekly telephone reporting. There were 1,829 illnesses reported. Research staff conducted home visits on a random sample of participants with telephone reports of medication use and the telephone reports were 93.7% accurate (95% CI 86.9%-97.4%).

